9.3 Analysis of the Primary Outcome

The intervention effect on opioid use over time will be assessed using a linear mixed model for repeated measures (MMRM) using categorical time effects (ref: S Davis). The model will be used to generate point and interval estimates and to test differences in mean changes in opioid dose between the 2 intervention groups at 12 months (primary timepoint) and 6 and 18 months (secondary timepoints). While the primary and secondary time assessments are at 6, 12 and 18 months, all available opioid prescription data from baseline (3-month average before randomization) through 18 months will be included in the model. The model will include fixed effects for the intervention group, time interval (as a categorical variable for **3, 6, 9, 12, 15 and 18**), intervention-by-time interaction, baseline opioid dose, and the stratification effect of institution (see model statement below). For each of the post-baseline timepoints, the daily MED is the average of the time from the end of the prior interval (i.e., 12 months is the 3-month average between 9 and 12 months). (Note: an inconsistency in the protocol inaccurately lists these intervals in protocol section 5.3.1, but they are accurately listed in Protocol Section 5.2.1).

This approach will provide consistent estimates and valid inferences under missing at random (MAR) data assumptions while accounting for correlation among multiple measures on the same participant. This mixed model will improve the power of the study and the precision of all estimates by allowing all available measures for an individual to be incorporated in the analysis, even if other timepoints are missing. An intervention-arm-specific Toeplitz correlation structure will be assumed for the within-participant measures, to reflect the changing correlation of these measures over time and permit the correlation structure to differ between study arms. Note: if this model does not converge, then a Toeplitz (not intervention-specific) structure will be fit. This model is further described below:

$$Y_{ij} = \alpha + \beta_1 Time_{ij} + \beta_2 Site_{ij} + \beta_3 Intervention_{ij} + \beta_4 BaselineOpioidDose_{ij} + \beta_5 (Intervention \times Time)_{ij} + \epsilon_{ij}$$

Where Y_{ij} is the j th measure of opioid dose in subject i , α is the intercept, β_1 through β_5 are coefficients, and ϵ_{ij} is the residual error term, and the variance-covariance matrix of the residual error terms for an individual is structured with the Toeplitz pattern such that all timepoints have the same variance estimate and all timepoints the same distance apart have the same correlation (i.e., the correlation between months 6 and 9 is assumed to be the same as the correlation between 9 and 12). Note that the protocol specified a random subject effect, but adding a random subject effect does not modify the model or model results in any way and so is excluded.

Statistical analysis modeling will be carried out utilizing SAS/STAT PROC MIXED (Littell, Milliken, Stroup, Wolfinger, & Schabenberger, 2006) with the general structure of the SAS code for this model shown below. Adjusted estimates of the change in opioid dose at each timepoint between the two interventions and corresponding 95% confidence intervals will be produced. The study's primary hypothesis will be tested by estimating the difference in the change in MED between the two intervention arms at 12 months. The study's secondary hypothesis will also be tested and associated effects estimated with the difference in LS means which estimates the average difference in the response outcome between the two intervention arms at each timepoint.

```
proc mixed data = INSPIRE_Primary method=REML;
class Unique_ID Intervention timepointN clinic
model change_OpioidDose_MED = Intervention timepointN clinic baseopioid
intervention*timepointN /s residual DDFM=KR;
repeated timepointN / type=toep group=intervention subject=Unique_ID
R RCORR;
```

```
LSMestimate 'MI-CBT vs SDM at 12 Mon'
  intervention*timepointN 0 0 0  1 0 0
                           0 0 0 -1 0 0 / CL;
  lsmeans intervention*timepointN/ diff pdiff CL;
run;
NOTE: Variable names may differ in the actual data.
```

Note: As specified in the protocol, the distribution of opioid doses will be evaluated prior to finalizing the analysis plan, and if opioid dose change from baseline is determined to be highly skewed and substantially non-normal, then opioid doses will be transformed to the natural log scale prior to subtracting baseline. The difference of logs will be modeled, the resulting estimates will be exponentiated back to the regular scale, and thus the primary analysis will compare the intervention arms based on the *relative* dose change, interpreted as the ratio of the post-baseline dose to the baseline dose. The analysis will be completed on either the change from baseline or the ratio relative to baseline, but not both. An evaluation of the distribution of change from baseline in MED was completed after the second CDM transfer. Data was found to be essentially normally distributed, and so analysis based on the ratio scale will not be completed.

Residual plots will be output to assess model assumptions/diagnostics.

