#### 5.3.1 Primary Analysis Methods for Opioid Usage Outcome

For reduction in opioid use, we will use a constrained linear mixed model to generate point and interval estimates of the reduction in opioid dose MED from baseline to **4, 6, 8, 10, 12, 14, 16, and 18** months and to test the hypothesis that this reduction differs between the 2 intervention arms. While the primary and secondary time assessments are at 6, 12 and 18 months, all available opioid prescription data from baseline through 18 months will be included in the model. This approach will provide consistent estimates and valid inferences under missing at random (MAR) data assumptions while accounting for correlation among multiple measures on the same participant. This mixed model will improve the power of the study and the precision of all estimates by allowing all available measures for an individual to be incorporated in the analysis, even if other timepoints are missing. The model will include fixed effects for the treatment group, time interval (as a categorical variable), treatment-by-time interaction, baseline opioid dose, the stratification effect of institution, and random effects for participant. An intervention-arm-specific Toeplitz correlation structure will be assumed for the within-participant measures, to reflect the changing correlation of these measures over time and permit the

correlation structure to differ between study arms. The model will be used to generate point and interval estimates and to test differences in mean changes in opioid dose between the 2 intervention groups at 12 months (primary timepoint) and to generate point and interval estimates at 6 and 18 months (secondary timepoints).

This model treats missing data as ignorably missing, assuming any missing data are missing at random, after accounting for baseline opioid dose. Sensitivity analyses based on multiple imputation procedures will be performed to evaluate departures from critical distributional and missing data assumptions. Plans to address missing data are further presented below (see *Missing Data Section*) and will be described in detail in the Statistical Analysis Plan. Assessments of model assumptions and goodness-of-fit will also be specified in the Statistical Analysis Plan.

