## 5.4 Sample Size and Power

*Cross-reference: UNC IRBIS Application Section A.8.3.*

Sample size estimates were generated to provide robust power to detect minimal clinically important differences (MCID) in reduction of opioid use between the 2 study arms.

Based on anecdotal information from the clinics participating in the study and data available from the Liebschutz and Sullivan et al. studies, a reasonable estimate of mean baseline opioid use across the planned study is 55 mg/day. Based on doses of this magnitude, providers involved with the study indicated that differences in dose reduction of 10 MED or greater were likely to be viewed as clinically meaningful. Consequently, sample size estimates were generated based on an effect size of a difference of 10 MED between the 2 intervention arms. The data available from the Liebschutz and Sullivan et al. studies indicate that a reasonable estimate of the coefficient of variation (ratio of standard deviation to the mean) for opioid dose levels is 1.45 (range of 1.19 to 1.54), suggesting that a reasonable estimate for the standard deviation of the dose level for this study is 80 MED. Finally, data from Liebschutz and Sullivan et al. suggest that correlation between the baseline and follow-up opioid use levels will result in a standard deviation of the change in opioid use of the same magnitude of the baseline standard deviation, and that controlling for baseline opioid use in an Analysis of Covariance model will reduce the residual mean square error for the test of treatment differences in the change in opioid use to no more

than 50% of the baseline level, or 40 mg/day. Based on these assumptions and an assumed minimally important difference of 10 mg/day, the number of evaluable independent participants required to achieve 80% power to detect a difference of this size is approximately 253 per study arm (total of 506), assuming no attrition.

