6. SAMPLE SIZE DETERMINATION

Sample size estimates were generated to provide robust power to detect minimal clinically important differences (MCID) in reduction of opioid use between the 2 study arms.

A total sample size of 506 participants (253 per study arm) will provide 80% power to detect an effect size of a difference of 10 MED between the SDM and MI+CBT intervention arm using an analysis of covariance model with $\alpha=0.05$ and assuming a baseline model-adjusted standard deviation for change from baseline of 40 MED. The sample size was inflated by 20% (608 total participants; 304 per study arm) to account for potential variance inflation associated with CBT group delivery (based on a group

size of 8 and an interclass correlation coefficient of 0.01) and a potential loss of follow-up opioid prescription data on as many as 12% of participants.

For the PROMIS secondary outcome measures, the minimally important difference (MID) for the physical function scale is 2 units, whereas the MID for the pain interference scale is 3.5 units. For both instruments, we assume the standard deviation for change from baseline is 10 (see section 9.2 for a more thorough description of these secondary measures). With the planned total of 608 randomized participants and assuming 20% of those have missing PROMIS scale responses, the power for the PROMIS Pain Interference score is 96%, while the power for the PROMIS Physical Functioning scale is 57% (Table 6.1).

Note that the enrollment was slower than planned, and due to timeline constraints was stopped prior to reaching 608 randomized participants. Final study enrollment was 526 randomized participants. As of June 2023 (DSMB report), study discontinuation was at 20%;, but survey completion rate was tracking around 60% (40% missing, higher than the planned levels). Approximate post-hoc power based on the final sample size is provided in Table 6.1.

Table 6.1. Power for Primary and Key Secondary Outcomes

Total sample size	Primary aim: Power for opioid MED ¹	Secondary aim: power for PROMIS Pain Interference ²	Secondary aim: Power for PROMIS Physical Functioning ²
Planned 608	80%	96%	57%
Approximate post hoc power based on randomized (n=526)	75% based on protocol- assumed level of missing opioid prescription data	85% Based on number of completed surveys	40% Based on number of completed surveys

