9.2 Variable Definitions

The table below provides a description of the study endpoints and subgroup categories, including data type and derivation. More information regarding these variables is provided in the analysis dataset specification file.

Variable	Type	Definition
Primary Outcome		
Change in opioid dose (based on average daily MED) from baseline to 12 months post-randomization	Continuous	
The primary outcome will be derived from EHR data from the Mid-South CDRN data warehouse. Total morphine equivalents for each prescription will be calculated by multiplying the quantity of each prescription by the strength of the prescription (milligrams of opioid per unit dispensed). The quantity-strength product is then multiplied by conversion factors to estimate the milligrams of morphine equivalent to the opioids dispensed in the prescription. The total average dose in morphine equivalents per day supplied is calculated by summing the morphine equivalents for each prescription filled during a given period and dividing by the number of days supplied. The below algorithms further describe derivation of the primary outcome measure:
 $\text{One Prescription's MED Daily (MEDD)} = \frac{(\text{Strength per unit}) \times (\text{Quantity dispensed}) \times (\text{MME Conversion factor})}{(\text{Days Supply})}$ $\text{Avg. MEDD per Timeframe} = \frac{(\text{Multiply each RX's MEDD by Days Supply}) \text{ then } (\text{Sum all RX's Total MEDD for those prescriptions within timeframe})}{\text{Total number of days in timeframe}}$ 
Opioid dose will be calculated as the prescribed milligrams of daily MED averaged over the 90 days prior to randomization and averaged over 90-days for the time periods of 3, 6-, 9-, 12-, 15- and 18-months post randomization.
 
We expect no missing prescriptions, yet some participants might not have complete data because (a) they discontinued and removed consent to use data after that date, (b) they were lost to follow-up and may have moved out of the clinic's care, (c) the last CDM transfer did not contain their data up to 18 months past baseline or (d) they discontinued taking opioids. Cases of (d) will be identified by the response to the T2 and T3 survey item G20 "Are you currently taking an opioid medicine now?". If the response indicates "no" and opioid prescriptions last dose date ends before month 18, then an MED of zero will be assumed for all days after the last dose date to Month 18 (or date participant removed informed consent, if applicable). Otherwise, if there is not a "no" response

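### The primary model holds residual variance constant from month 3 to month 18 in each arm without justification; if variance differs by visit the 12-month standard error is wrong, in a direction the documents do not settle

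*SAP*

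**What the plan says.** Protocol 5.3.1 sets the structure and its reason together: "An intervention-arm-specific Toeplitz correlation structure will be assumed for the within-participant measures, to reflect the changing correlation of these measures over time". It adds that the structure may differ between arms.

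SAP 9.3 repeats that choice with the same reason, "to reflect the changing correlation of these measures over time", and spells out the consequence: "all timepoints have the same variance estimate and all timepoints the same distance apart have the same correlation". The SAS code matches, with TYPE=TOEP and GROUP=intervention on the REPEATED statement. Each arm therefore has one residual variance for months 3, 6, 9, 12, 15 and 18. On convergence failure, "if this model does not converge, then a Toeplitz (not intervention-specific) structure will be fit". That fallback drops the arm difference but still has one variance over time.

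Other features of SAP 9.3 matter here:

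- Inference uses DDFM=KR with no EMPIRICAL option, so the standard error is model-based.
- One baseline slope serves all visits.
- Residual plots and the R and RCORR matrices are to be output, but nothing says what follows from them.

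Baseline is the same kind of measure as the outcome. SAP 9.2 says "Opioid dose will be calculated as the prescribed milligrams of daily MED averaged over the 90 days prior to randomization", and each later window is also a 90-day average.

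**The concern.** A Toeplitz structure lets correlation depend on the distance between visits. It says nothing in favour of equal variances, and neither document offers another reason for them.

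The outcome is change from baseline, adjusted for baseline, and baseline is an earlier window of the same dose measure. If correlation between windows fades with distance, baseline explains less of each later window. Residual variance then rises by visit, unless the dose variance itself falls enough to offset this. A single pooled variance would be too large for early visits and too small for late ones. Month 12 is the fourth of six visits, so its error depends on the shape of the fade.

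The 12-month contrast is the single primary formal test (SAP 7.6), and this standard error decides it. The 6- and 18-month intervals come from the same model. SAP 9.6.4 and 9.6.5 reuse the structure for subgroups.

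**Working it through.** **Inputs from the documents.** Protocol 5.4 states that "a reasonable estimate for the standard deviation of the dose level for this study is 80 MED" and expects "a standard deviation of the change in opioid use of the same magnitude of the baseline standard deviation". SAP 6 works by "assuming a baseline model-adjusted standard deviation for change from baseline of 40 MED". SAP 6 reports 526 randomized, about 263 per arm. Protocol 5.3.3 allows up to 12% missing MED at 12 months. The test is two-sided at 0.05.

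**The plan's own figure.** n per arm = 2 × (1.960 + 0.842)² × 40² / 10² ≈ 251.2, or 252 by the normal approximation. The noncentral t gives 253 (power 80.1%). Then 506 × 1.2 = 607.2, rounded up to 608. The sample size reproduces and is not at issue.

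**Correlation with baseline at month 12.** With equal dose SDs, residual SD = 80 × √(1 − r²). Setting this to 40 gives r = 0.866. Taking the SD of change as equal to the baseline SD gives 2 × 80² × (1 − r) = 80², so r = 0.5. Both values were used.

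**One worked case (assumed steady autoregressive fade).** Let r(t) = 0.866^(t/12), with dose SD 80 throughout.

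1. With common baseline slope b, residual variance at month t is 80² × [1 − r(t)² + (r(t) − 1 − b)²]. The fitted b is about −0.11.
2. For month 3, r = 0.965, so the SD is 80 × √(0.0694 + 0.0056) ≈ 22. The six SDs are 22, 30, 35, 40, 44 and 48.
3. The best-fitting Toeplitz has one SD of about 37, against 40 actually present at month 12.
4. With 263 per arm and monotone dropout reaching 12% by month 12, the reported SE is 3.33 and the true SE 3.64. The ratio is 0.914, so the SE is 8.6% too small.
5. Type I error = 2 × [1 − Φ(1.96 × 0.914)] = 2 × [1 − Φ(1.791)] ≈ 7.3%.
6. Coverage of the 95% interval is 98.5% at month 6 and 86.9% at month 18.

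**Other assumed patterns.** Same method, 12% missing unless stated; the two values of r are 0.866 and 0.5.

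| Assumed pattern | 12-month type I error |
|---|---|
| Constant residual variance | 5.0% |
| Steady autoregressive fade, r = 0.866 / 0.5 | 7.3% / 7.0% |
| Same, r = 0.866, no missing data / 24% missing | 6.8% / about 8% |
| Linear fade | 6.7% to 7.2% |
| Early fade then plateau, 12% / 24% missing | 8.1% / 8.4% |
| Steady fade, r = 0.866, with 25 / 50 / 75% of the correlation loss as visit noise | 6.6 / 6.0 / 5.5% |
| Same, r = 0.5 | 6.3 / 5.8 / 5.3% |
| Steady fade, dose SD falling 80 to 60 by month 18, r = 0.866 / 0.5 | 6.7% / 6.6% |
| Fade mainly after month 12, dose SD 80 | 2.0% to 3.4% (SE ratio 1.19 to 1.085) |
| Residual SD set directly, rising 30 to 45 | 5.9% |
| Residual SD set directly, falling 45 to 30 | 3.6% to 3.8% |
| Residual SD set directly, 30, 38, 42, 40, 36, 32 | 7.7% to 8.9% |

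If dose SD halves from 80 to 40 by month 18, the SE is 1% to 4% too large.

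**Finite-sample check.** REML simulation used 263 per arm, 12% missing, site omitted, and 4,000 to 5,000 replicates (Monte Carlo error about 0.3 points). Rejection at month 12, Toeplitz against unstructured:

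- Steady fade to 0.866: 7.9% against 5.5%. Mean reported SE against empirical SD was 3.34 against 3.68 for Toeplitz, and 3.70 against 3.73 for unstructured.
- Falling SD, 45 to 30: 3.1% against 4.5%.
- Constant SD 40: 5.2% against 5.5%.

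All fits converged.

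**The case against.** The strongest reply is that the direction is not established. A reader might infer from the worked case that the primary test is anticonservative. The documents do not support that: they give no SD or correlation by visit. At constant dose SD, a fade that comes mainly after month 12 makes the standard error too large, so the excess can vanish or reverse without any fall in dose variance. This stands in full.

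Second, the 7% to 8% figures for fading correlation assume no visit-to-visit noise, and the documents point to some. SAP 9.2 sums prescription totals falling in a window and divides by the days in it, and Protocol 5.2.3 describes prescriptions as generally 30 days. SAP 5.2 anticipates baseline averages under 20 MED in people whose latest prescription qualified, and SAP 9.2 has a zero-MED baseline category. Such noise flattens residual variance across visits and shrinks the excess. This also stands, though the amount of noise is unknown.

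Third, the multiple-imputation ANCOVA in SAP 9.4 does not use the pooled variance, and it is triggered by a significant result, where a false positive would matter. SAP 6 reports 20% study discontinuation, so the trigger might be reached, although discontinuation is not the same as missing MED. It is a partial answer only: it needs both conditions, it was designed for data missing not at random, and it cannot help if an oversized standard error made the primary result nonsignificant.

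Fourth, Toeplitz is a recognised structure, prespecified in the protocol, and the SAP states the equal-variance assumption openly. A reader might infer that the SAP contradicts itself. It does not: correlation can vary with lag while variance stays constant. What is missing is a reason for the second assumption and a safeguard if it fails.

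**Conclusion.** The concern holds as a conditional weakness in the primary analysis, not as a demonstrated bias. The restriction, its retention in the fallback, the narrow rationale and the lack of any unconditional check are all plain in SAP 9.3 and 9.4. The consequence depends on how residual variance moves across visits, which the documents do not report.

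For a steady or early fade, the standard error is too small and the error moderate; the 8.4% upper end needs an early fade with 24% missing. For a late fade or steadily falling residual SD, the test is conservative and loses power in a trial the SAP already puts at about 75%. The most extreme figure, 8.9%, comes from a rise-then-fall SD pattern that was simply assumed. If variance is constant there is no error. Every figure other than the constant-variance one rests on an assumed pattern and shows sensitivity; none predicts this trial's result.

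The change is worth making because it protects the single primary test whichever way the variance moves, at little cost.

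**What to change.** In SAP 9.3, prespecify TYPE=UN with GROUP=intervention. If it does not converge, use heterogeneous Toeplitz (TOEPH) by arm, and only then TOEP. Choose by convergence alone, not by inspecting the arm comparison. Use the same order in SAP 9.6.4 and 9.6.5.

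The cost is a short edit to text and code, and more covariance parameters. Over two arms with six visits, UN has 2 × 21 = 42, TOEPH 2 × 11 = 22, and TOEP 2 × 6 = 12. With 526 participants this is supportable. With constant variance, the simulation showed no loss of precision (mean 12-month SE 3.63 under both structures). In the fading-correlation cases the unstructured estimate was 0.2% to 3.2% more variable than the Toeplitz one, but its reported standard error was correct.
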